Participants are randomized (stratified by sex and cohabiting status) into one of two groups: an exercise training group or a control group. The exercise training group will again be randomized to either high-intensity training or moderate-intensity training. Spouses/partners will be randomized into the same group. The randomization will be performed after the completion of all basic examinations at examination 1. The Unit for Applied Clinical Research at NTNU is developing a web-based randomization procedure to ensure impartial assignments. After randomization, participants will receive verbal and written information about how to exercise and record their training.

Sample size and statistical power

The primary endpoint of the study is overall mortality. According to Statistics Norway, approx. 2% in this age group die every year. Currently, there is no data that indicates the magnitude of the effect of exercise on the reduction in mortality, but from observational studies a 50% reduction has been reported. With a 50% reduction in mortality rate, and a power of 90% (p<0.05), 1200 participants are needed (600 in each group). We will try to include 1500 participants to allow for drop-out (approximately 20%).

Intervention

Choice of intervention

Clinical studies have shown that high-intensity exercise training gives a greater increase in VO_{2max} and better cardiovascular adaptations than low- or moderate-intensity training (20, 22, 23). However, little research has been done on an elderly population, and it is unknown which intensity gives the greatest effect on morbidity, mortality and functional capacity in this group. Therefore, we believe that it is important to compare individuals who exercise at moderate and high intensities. Additionally, we think it is important to have a control group that receives current recommendations for physical activity.

High-intensity training group

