The original plan was not very specific on how the analysis would be performed; thus, a more detailed plan was formed before (13 February 2019) any analysis was conducted. For the VO_{2peak} and SF 8 we plan to use a linear mixed model with the clinical variables one at a time as dependent variable. Time point (0,1,3,5 years), intervention group, and their interaction as categorical covariates, and participant nested within cohabiting pair as random effects. Participants had been randomized such that a cohabiting pair was randomized to the same group. Hence, it is appropriate to use a three-level mixed model, with participant nested within cohabiting pair. In addition, we adjust for variables used as stratification variables in the randomization (sex, cohabitation status). We will adjust for age at inclusion, which is plausibly important prognostic factor, as recommended by (25) and (26). In the mixed model, we will adjust for baseline as recommended by (27). Normality of residuals will be checked by visual inspection of QQ plots. In these analyses, if a person is dead, we regard that as missing data after the person is dead. In a sensitivity analysis, we will exclude the persons who died during the study from the analysis. The main analysis for survival, will be a Cox proportional hazards regression, adjusting for the covariates listed above.

Summary of changes Statistical analysis plan

The following amendments to the original statistical analysis plan have been made.

• Amendment No1; Exclusion of VO_{2peak} data

Amendment No1:

Participants should have been tested on the same machine (treadmill or bike) at every examination. For those who had test both on treadmill and bike, we deleted the bike measurements. In total 41 persons had data both from treadmill and bike, bike measurements were deleted, and values given as missing.

References

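### The primary Cox model makes no allowance for cohabiting pairs randomised together, so its confidence interval and p-value may be slightly anti-conservative

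*Supplement*

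**What the plan says.** The final protocol, under Randomization, stratifies by sex and cohabiting status and adds: "Spouses/partners will be randomized into the same group". Under Sample size and statistical power it states: "The primary endpoint of the study is overall mortality".

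The final SAP repeats the design feature, "Participants had been randomized such that a cohabiting pair was randomized to the same group", and draws a conclusion from it: "Hence, it is appropriate to use a three-level mixed model, with participant nested within cohabiting pair". That conclusion belongs to the linear mixed model for VO2peak and SF 8, where the pair is a random effect. The SAP then adds fixed adjustment for the stratification variables (sex and cohabitation status) and for age: "We will adjust for age at inclusion, which is plausibly important prognostic factor".

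Survival is covered by the closing sentence of the section: "The main analysis for survival, will be a Cox proportional hazards regression, adjusting for the covariates listed above". Neither the final SAP nor the final protocol gives a frailty term, a clustered variance or a pair-level sensitivity analysis for mortality.

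**The concern.** The SAP's reason for modelling the pair is how allocation was done, not the type of outcome. It applies to survival as much as to VO2peak, yet the primary analysis is where it is not carried through.

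A fixed effect for cohabitation status does not fill the gap. It shifts the average hazard of all cohabiting participants and says nothing about whether two particular partners tend to share an outcome. When both members of a positively correlated pair are in the same arm, the variance of the log hazard ratio exceeds what an ordinary Cox fit reports. At stake are the width of the primary confidence interval and the size of the primary test. The estimated hazard ratio is not in question.

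**Working it through.** **1. The plan's own figure.** The inputs, from the final protocol's sample size section, are about 2% mortality a year, a 50% reduction, 90% power and p<0.05. The horizon is 5 years (Objectives). Taking 5 × 2% = 10% against 5%, two-sided:

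- Comparison of two proportions without continuity correction: 582 per arm, 1164 in total. Power at 600 per arm is 0.909.
- Schoenfeld's formula with hazard ratio 0.5: 4 × (1.960 + 1.282)² / (ln 0.5)² = 87.5, so 88 events. At a mean risk of 7.5%, 88 / 0.075 gives 1174 participants.
- Drop-out: 1200 / (1 − 0.20) = 1500.

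Both totals are within 3% of the stated 1200, and both treat participants as independent.

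**2. Effect of pairing on the variance.** Let f be the share of participants enrolled as pairs and ρ the within-pair correlation of the outcome. With partners always in the same arm and clusters of size two or one:

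- design effect D = 1 + fρ
- the true standard error is √D times the model-based one
- true type I error = 2 × [1 − Φ(1.96 / √D)]

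The documents give neither f nor ρ. Every value below is an assumption.

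**3. From frailty variance to correlation.** Under a shared gamma frailty with variance θ and a marginal five-year risk of 10%, let u = 0.9^(−θ) − 1. Joint survival of a pair is (1 + 2u)^(−1/θ), and ρ = (joint survival − 0.81) / 0.09.

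| θ | joint survival | ρ |
|---|---|---|
| 0.25 | 0.8122 | 0.02 |
| 1 | 0.8182 | 0.09 |
| 2 | 0.8250 | 0.17 |

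At θ = 2, one partner's death multiplies the other's hazard by 1 + 2 = 3, which is a very strong dependence.

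**4. Results by formula.**

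| f | ρ | D | √D | type I error |
|---|---|---|---|---|
| 0.3 | 0.02 | 1.006 | 1.003 | 5.1% |
| 0.3 | 0.05 | 1.015 | 1.007 | 5.2% |
| 0.3 | 0.09 | 1.027 | 1.013 | 5.3% |
| 0.6 | 0.17 | 1.10 | 1.05 | 6.2% |
| 0.7 | 0.17 | 1.12 | 1.06 | 6.4% |

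At f = 0.3 and ρ = 0.05, the number equivalent to 1200 independent participants is 1200 × 1.015 = 1218. Power with 1200 falls from 0.909 to 0.905, so the sample size is barely touched.

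**5. Simulation.** Null trials used 1500 participants, 2% mortality a year, 5 years of follow-up, pairs allocated together and gamma frailty, with 4000 replicates per setting. The unadjusted log-rank (Cox score) test was compared with ordinary and with pair-clustered variance. Monte Carlo standard error is √(0.05 × 0.95 / 4000) = 0.0034.

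| f | θ | ordinary | pair-clustered |
|---|---|---|---|
| 0.3 | 0 | 0.050 | 0.050 |
| 0.3 | 0.5 | 0.045 | 0.044 |
| 0.3 | 1 | 0.056 | 0.052 |
| 0.5 | 0.5 | 0.055 | 0.051 |
| 0.5 | 1 | 0.052 | 0.048 |
| 0.7 | 1 | 0.056 | 0.047 |
| 0.7 | 2 | 0.064 | 0.051 |

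Up to θ = 1, every ordinary-variance result lies within two Monte Carlo standard errors of 0.05. Only the last setting is clearly above it. A separate run of 6000 replicates with f = 0.6 and θ = 2 gave 6.2% with ordinary and 5.3% with pair-clustered variance. Simulation and formula agree.

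**The case against.** The strongest objection is size. Clusters have at most two members, only some participants are paired, and deaths are uncommon over five years. At moderate settings the simulation cannot separate the ordinary test from its nominal level. The simulated test was also unadjusted, whereas the planned model adjusts for age, sex and cohabitation status. If partners are close in age, that adjustment removes some of the correlation, and the figures above would then overstate what remains. This objection stands, and it limits the point to a modest one.

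A second objection is that the survival sentence is merely brief, and that its reference back to the listed covariates might take in the pair. That is strained: the SAP names the pair as a random effect, separately from the covariates, and a Cox model has no pair term unless a frailty or cluster option is stated. If one was intended, the sentence still needs to say so, because two analysts could follow it and report different intervals.

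A reader might infer more than the text supports. The SAP calls pair-level modelling appropriate for the linear outcomes; it does not say that it is required in every model. Nor do the documents show that within-pair correlation in survival is positive, so they do not establish that the type I error is above 5%. That is conditional on an assumption, though a reasonable one to protect against.

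**Conclusion.** As written, the primary model's standard error does not reflect the randomisation used, and this departs from the SAP's own reasoning for VO2peak and SF 8. That textual gap is clear. Its consequence is conditional and probably small: if 30% of participants are in pairs and the within-pair correlation is 0.02 to 0.09, the standard error should be about 0.3% to 1.3% larger and the type I error is about 5.1% to 5.3%. Figures of 6.2% to 6.4% need 60% to 70% in pairs together with a frailty variance of 2.

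It would be wrong to conclude that the primary result is unreliable or the hazard ratio biased. The gap could matter for a p-value close to 0.05 or a confidence limit close to 1, but is unlikely to overturn a clear result. It should be fixed because a variance that is valid whatever the correlation is readily available, and choosing one after seeing the results would be a post hoc decision about the primary analysis.

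**What to change.** Add a sentence to the final SAP: the confidence interval and p-value for the primary Cox model come from a robust sandwich variance clustered on cohabiting pair, with participants enrolled without a partner as clusters of size one. Apply the same variance to any Cox models for the secondary event-time outcomes in Table 1 of the final protocol (cause-specific death, and development of cardiovascular disease and cancer). A Cox model with shared frailty by pair may be named as a sensitivity analysis. Reporting the number of pairs enrolled would let readers judge how much the clustering matters.

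The cost is one sentence and one software option. The hazard ratio estimate from the primary model is unchanged, and the only downside is a possibly slightly wider interval.
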